11.4.2.6 Plasma Biomarkers of Cardiac Injury, Inflammation, and Remodeling

The plasma biomarker C_{max} and AUC₀₋₄₈ will be derived from the plasma biomarker levels collected at the following timepoints: Predose, 1, 4, 12, 24 and 48 hours post-study drug. AUC₀₋₄₈ will be calculated using the linear trapezoidal method. Where possible, the derivation will be carried out using actual post-dose times recorded. If actual times are missing, nominal times may be used with sponsor approval. Maximum deviation defined as the largest magnitude shift (or absolute change) from baseline will be derived.

Summary statistics (also including geometric means and geometric CV%) for each plasma biomarker concentration will be produced by each treatment group and the overall FDY-5301 group for the values and its changes from baseline. The baseline is defined as the last actual value obtained prior to study drug infusion.

For each of these plasma biomarker concentrations, a single pairwise comparison will be performed by timepoint to analyze change from baseline value between all three FDY-5301 groups (overall) and placebo. An unpaired Student's T-test will be used for the pairwise comparison if the data are normally distributed and a Mann-Whitney rank test will be used for nonparametric data. Normality will be assessed based on the Shapiro-Wilk test at the 5% level.

Each group will then be tested using a one-way ANOVA to obtain a common variance followed by a Dunnett's post-test to separately compare each FDY-5301 dose group to placebo.

The logarithmically transformed C_{\max} , AUC_{0-48} and maximum deviation from each group will be tested using a one-way ANOVA to obtain a common variance followed by a Dunnett's post-test to separately compare each FDY-5301 dose group to placebo.

The arithmetic least squares means of the treatment differences will be back-transformed to provide the geometric means and its 95% confidence interval.

The same summarization and statistical analyses for plasma biomarker concentrations and parameters will be repeated by baseline TIMI flow (grade 1 and lower, or, grade 2 and 3) and infarct type (anterior or other).

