12.2.5 Other Biomarkers of Cardiac Injury and Inflammation

Serum biomarkers of cardiac injury, inflammation and remodeling will be measured at the following time points:

- Pre-study drug
- 1,4,12, 24 and 48 hours post-study drug
- 3 months post-study drug

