3 ABBREVIATIONS

Abbreviations pertain to the SAP only (not the TFLs).

ADaM	analysis data model
AE	adverse event
AMI	acute myocardial infarction
ANOVA	analysis of variance
ATC	Anatomical Therapeutic Chemical
AUC	area under the curve
AUC _{inf}	area under the concentration-time curve extrapolated to infinity
AUC _{last}	area under the concentration-time curve from time 0 to the time of the last observed quantifiable concentration
AV	Atrioventricular
BLQ	below the limit of quantification
BPM	beats per minute
CDISC	Clinical Data Interchange Standards Consortium
CL	total body clearance
C _{max}	maximum observed plasma concentration
CMR	cardiac magnetic resonance
CRF	Case Report Form
CSR	Clinical Study Report
CV%	coefficient of variation
ECG	electrocardiogram
EDV	end-diastolic volume
EF	ejection fraction
ESV	end-systolic volume
FS	fractional shortening
ICH	International Conference on Harmonisation
INF	infarct size
ITT	intent-to-treat

Kel	apparent terminal elimination rate constant
LLOQ	lower limit of quantification
MedDRA	Medical Dictionary for Regulatory Activities
MRI	magnetic resonance imaging
MSI	myocardial salvage index
NC	not calculated
NR	no result
PCI	percutaneous coronary intervention
PK	pharmacokinetics
PP	per protocol
SAP	Statistical Analysis Plan
SD	standard deviation
STEMI	ST-segment elevation myocardial infarction
T _{1/2}	apparent terminal elimination half-life
TEAE	treatment-emergent adverse event
TFLs	tables, figures, and listings
T _{last}	time of last quantifiable concentration
T _{max}	time when maximal concentration is achieved
V _{ss}	volume of distribution at steady-state
VV	ventricular volume
V _z	volume of distribution during the terminal elimination phase
WHO	World Health Organization

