For multiple peaks, the highest postdose concentration will be reported as C_{max}. In the case that multiple peaks are of equal magnitude, the earliest T_{max} will be reported.

11.6.2 Criteria for Handling Concentrations Below the Limit of Quantification in Pharmacokinetic Analysis

- Concentration values that are below the limit of quantification (BLQ) will be set to zero, with defined exceptions as follows;
 - Any embedded BLQ value (between 2 quantifiable concentrations) and BLQ values following the last quantifiable concentration in a profile will be set to missing for the purposes of PK analysis.
 - If there are late positive concentration values following 2 BLQ concentration values in the apparent terminal phase, these values will be evaluated. If these values are considered to be anomalous, they will be set to missing.
 - If an entire concentration-time profile is BLQ, the profile will be excluded from the PK analysis.
 - If a predose concentration is missing, it may be set to zero with sponsor approval.

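### Biomarker Cmax is drawn from a sample list that includes predose, which can pull its comparison toward the null for any marker that does not clearly rise after dosing

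*SAP*

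**What the plan says.** Protocol 12.2.5 schedules biomarker samples before study drug, at "1,4,12, 24 and 48 hours post-study drug", and at 3 months.

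SAP 11.4.2.6 uses the predose-to-48-hour samples as one list for two parameters: biomarker Cmax and AUC0-48 both "will be derived from the plasma biomarker levels collected at the following timepoints: Predose, 1, 4, 12, 24 and 48 hours post-study drug". Nothing in that section limits Cmax to postdose samples. The SAP abbreviation list (section 3) gives Cmax as the "maximum observed plasma concentration", also without such a limit.

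For iodide, SAP 11.6.1 states that with multiple peaks "the highest postdose concentration will be reported as" Cmax. That rule belongs to the pharmacokinetic section.

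The predose sample is also the biomarker baseline: "The baseline is defined as the last actual value obtained prior to study drug infusion". Cmax and AUC0-48 are log-transformed and tested together with a third parameter: the "maximum deviation from each group will be tested using a one-way ANOVA to obtain a common variance followed by a Dunnett's post-test", each dose against placebo. No baseline covariate is mentioned. The same section also plans, for the concentrations themselves, that "a single pairwise comparison will be performed by timepoint to analyze change from baseline value", pooled FDY-5301 against placebo, followed by ANOVA and Dunnett by dose.

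**The concern.** AUC0-48 needs a time-zero value, so predose belongs in its list. A peak response to treatment does not need one. If the list is applied as written, biomarker Cmax is the maximum over predose and the five postdose samples, and in some patients that maximum precedes treatment.

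Protocol 6.1 admits patients up to 12 hours after symptom onset, so a marker could already be on a plateau or declining at dosing. If the drug lowers postdose levels, predose becomes the maximum more often in treated patients, and the Cmax contrast shrinks. At stake is the reading of one tested biomarker parameter: a Cmax comparison showing little difference could partly reflect how the peak was defined.

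**Working it through.** **Inputs from the documents.** Six samples, one predose and five postdose (SAP 11.4.2.6). About 20 patients per arm (SAP 7: 1:1:1:1; SAP 9: placebo 20, combined active 60). The documents give no effect size, SD or power for biomarker Cmax, so there is no stated figure to reproduce.

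**Step 1: how often predose is the maximum.** For a flat marker with no drug effect the six values are exchangeable, so the probability is 1/6 = 16.7%.

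**Step 2: direction.** Let P be a patient's predose log level and M the highest postdose log level. If the drug lowers M by d, then max(P, M) falls by an amount between 0 and d. This holds for every patient, so including predose can never enlarge a one-directional effect and may shrink it.

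**Step 3: size (all values assumed).** Log level = patient effect N(0, 0.5) + profile + N(0, 0.3), with predose profile 0. Postdose profiles at 1, 4, 12, 24 and 48 h:
- flat: 0 throughout
- falling: -0.1, -0.3, -0.5, -0.6, -0.6
- rising: 0.2, 0.6, 0.8, 0.5, 0.2

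The drug multiplies every postdose level by 0.8 (log effect -0.223) or 0.63 (-0.462). With 200,000 simulated patients per scenario, the effect on log Cmax is:

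| Marker | Reduction | With predose | Postdose only | Ratio |
|---|---|---|---|---|
| Flat | 20% | -0.165 | -0.223 | 74% |
| Flat | 37% | -0.285 | -0.462 | 62% |
| Falling | 20% | -0.090 | -0.223 | 40% |
| Falling | 37% | -0.138 | -0.462 | 30% |
| Rising | 20% | -0.220 | -0.223 | 99% |
| Rising | 37% | -0.444 | -0.462 | 96% |

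For the flat marker, predose is the maximum in 17% of placebo patients, and in 37% (20% reduction) or 63% (37% reduction) of active patients. On the ratio scale, a true 37% reduction in a flat marker appears as 1 - exp(-0.285) = 25%. In the falling marker it appears as 1 - exp(-0.138) = 13%.

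**Step 4: later onset.** Step 3 gives the drug its full effect at the 1 h sample, so postdose-only Cmax recovers the effect by construction. With the same model and no effect before 4 h:

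| Marker | Reduction | With predose | Postdose only | Postdose only / true effect |
|---|---|---|---|---|
| Flat | 37% | -0.182 | -0.266 | 58% |
| Falling | 20% | -0.029 | -0.073 | 33% |
| Falling | 37% | -0.036 | -0.108 | 23% |

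With onset at 12 h, postdose-only Cmax recovers 7% to 12% in the falling marker. The 1 h sample then takes over as the early, unaffected maximum. With-predose to postdose-only ratios stay near those of Step 3 (for example 0.182/0.266 = 68% and 0.036/0.108 = 33%), but they become noisy when both effects are close to zero.

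**Step 5: other assumptions.** Take a 30% reduction at all postdose times, between-patient log SD 0.3 or 0.5, and within-patient log SD 0.1 to 0.4. The share of the log effect kept with predose included is then:
- flat: 35-72%
- falling to 0.7 of predose: 17-61%
- falling fast to 0.5: 1-38%
- rising 1.5-fold: 86-94%
- rising 5-fold: 100%

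**The case against.** The drafting has a benign reading. One sentence lists samples for two parameters, one of which needs predose, and the SAP's only operational Cmax rule is postdose. A programmer might carry that rule over. It is written for iodide, though, and does not formally govern biomarkers, so the ambiguity remains.

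Neither document names a biomarker or its time course. The 12-hour limit gives no distribution of arrival times, so a marker already falling at dosing is a possibility, not an established fact. This stands: the number of affected markers is unknown and could be zero.

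The stakes are also low. Protocol 14.1.3 and 14.1.6 treat the secondary efficacy outcomes as exploratory, no biomarker is powered, and the distortion is toward the null, so it creates no false positives. At about 20 v 20, the SE of a log Cmax difference in the Step 3 model is near 0.17. With a Dunnett critical value of about 2.41, a 20% reduction in a flat marker has about 8% power with predose and 15% without, which is inconclusive either way. For a 37% reduction with immediate onset, power goes from about 23% to 62%, but that gain depends on the immediate onset.

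A reader might infer that the biomarker analysis as a whole hides a drug effect, more so the better the drug works. The documents do not support that. Change from baseline by timepoint subtracts predose. Maximum deviation is measured from predose, whose own deviation is zero, so including it cannot alter the maximum. Both can show a postdose reduction that Cmax misses.

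**Conclusion.** The point holds as a minor one. Followed literally, SAP 11.4.2.6 allows a pre-treatment value to be reported as biomarker Cmax, and for markers that do not clearly rise this pulls the Cmax comparison toward the null. The direction follows from the definition. The size rests on assumed SDs, profiles and effects. With log SDs of 0.5/0.3 and a 20% or 37% reduction, the effect with predose is about 60-80% of the postdose-only effect for a flat marker, about 30-45% for a falling one and at least 96% for a clearly rising one.

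Two stronger conclusions might be drawn and should not be. One is that the peak is often a pre-treatment value: without a drug effect or a decline it is 1 patient in 6, and any higher rate depends on an assumption. The other is that dropping predose restores the full effect: that is true only if the drug acts fully by the first postdose sample. With onset at 4 h or later, postdose-only Cmax itself recovers only part of the effect in flat or falling markers. One exploratory parameter is affected, not the biomarker evidence as a whole.

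**What to change.** In SAP 11.4.2.6, define biomarker Cmax as the highest postdose concentration, from 1 to 48 hours, in line with the iodide rule in 11.6.1. Keep the predose value for AUC0-48 and as the baseline. Add that, for markers that do not rise after dosing, interpretation rests on the change-from-baseline analyses and not on Cmax, since a peak is a weak summary of such a marker under either definition.

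The cost is a sentence or two, made before database lock, by which time SAP section 4 requires the plan to be final. No new data are needed, and clearly rising markers are essentially unaffected.

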11 STATISTICAL METHODOLOGY

11.1 General

Data listings will be provided for the ITT Population. Summary statistics and statistical analyses will be performed for patients included in the relevant analysis populations.

For continuous data, summary statistics will include the arithmetic mean, arithmetic standard deviation, median, minimum, maximum, and number. For log-normal data (eg, the PK parameters: AUCs and maximum observed concentration [C_{max}]), the geometric mean and geometric coefficient of variation (CV%) will also be presented. For categorical data (i.e. ST-segment resolution and persistent arrhythmias), frequency counts, percentages and odds ratios will be presented, where applicable. Data listings will be provided for all patients up to the point of withdrawal, with any patients excluded from the relevant population highlighted. For the calculation of summary statistics and statistical analysis, unrounded data will be used.

Missing values will not be imputed.

Data analysis will be performed using SAS® Version 9.4 or higher.

Analysis Data Model (ADaM) datasets will be prepared using Clinical Data Interchange Standards Consortium (CDISC) ADaM Version 2.1, and CDISC ADaM Implementation Guide Version 1.1. Pinnacle 21 Community Validator Version 2.1.2 will be utilized to ensure compliance with CDISC standards.

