11.1.1 Definition of Baseline and Change from Baseline

Baseline for each parameter is defined as the last value measured prior to dosing, including repeat vital signs and unscheduled (clinical laboratory parameters) readings (see Section [11.1.2](#) for definitions of repeat and unscheduled readings).

Mean change from baseline is the mean of all individual patients' change from baseline values. Each individual change from baseline will be calculated by subtracting the individual patient's baseline value from the value at the timepoint. The individual patient's change from baseline values will be used to calculate the mean change from baseline using a SAS procedure such as Proc Univariate.

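### The log-transformed maximum biomarker deviation ignores direction: on the natural reading a fall and a rise of equal size score the same, and zero shifts have no rule

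*SAP*

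**What the plan says.** SAP 11.4.2.6 derives three parameters per plasma biomarker: Cmax, AUC0-48 and a maximum deviation. Cmax and AUC0-48 use samples at "Predose, 1, 4, 12, 24 and 48 hours post-study drug". For the third parameter the text is: "Maximum deviation defined as the largest magnitude shift (or absolute change) from baseline will be derived". The biomarker baseline is fixed: "The baseline is defined as the last actual value obtained prior to study drug infusion".

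All three parameters are then log-transformed and handled alike: "maximum deviation from each group will be tested using a one-way ANOVA to obtain a common variance". Dunnett comparisons of each dose with placebo follow, and then: "The arithmetic least squares means of the treatment differences will be back-transformed to provide the geometric means and its 95% confidence interval".

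Two general rules bear on this. SAP 11.1.1 makes change from baseline a signed difference, timepoint value minus baseline ("Each individual change from baseline will be calculated by subtracting the individual" patient's baseline from it). SAP 11.1 states "Missing values will not be imputed". The protocol does not define a maximum deviation, and SAP section 13 (changes from the protocol) does not mention it.

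**The concern.** Cmax and AUC0-48 are built from concentrations, cannot be negative, and suit a log scale. A change from baseline is a different kind of quantity: it can be positive, negative or zero. The SAP applies one log-scale analysis to all three.

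Direction matters here. Protocol 3.3 expects the drug to dampen the inflammatory response, and SAP 6.2.1 lists these biomarkers among the secondary efficacy outcomes. Falls from baseline are possible. Protocol 6.1 admits patients within 12 hours of symptom onset, so a marker may already be raised in the last predose sample. For such a marker a lower geometric mean of the maximum deviation could mean a smaller rise or a smaller fall, and a reader of the table could not tell which.

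**Working it through.** The plan gives no figure for this parameter, so there is nothing to reproduce. The check is on what the definition does to simple profiles.

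**1. Unsigned reading**, D = |C_t − C_0| at the time of largest shift, analysed as ln D:
- 100 to 40: D = |40 − 100| = 60, ln 60 = 4.094.
- 100 to 160: D = |160 − 100| = 60, ln 60 = 4.094.
- If every patient in one group followed the first profile and every patient in another the second, the geometric means would be 60 and 60, and their ratio 1.00.
- No shift at any time: D = 0, and ln 0 does not exist.

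**2. Signed reading**, D = C_t − C_0:
- 100 to 40: D = −60, no log.
- 100 to 160: D = +60, ln 60 = 4.094.
- Zero: no log.
- SAP 11.4.2.6 gives no offset, rank alternative or exclusion rule for non-positive values of this parameter.

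**3. Which reading does the text favour?** The definition speaks of magnitude and of absolute change, and a log is planned. All three point to an unsigned value. Absolute could also mean not expressed as a percentage, so the signed reading cannot be excluded, but it is the less natural one.

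**4. Illustration of the unsigned reading (assumed inputs).** The documents give no biomarker means or SDs. Suppose changes are normal in arbitrary units, with a patient SD of 0.7 and a noise SD of 0.7, at five post-dose times (200,000 simulated patients per mean shift):

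| Mean shift | Mean signed deviation | Geometric mean of unsigned deviation | Share with negative deviation |
|---|---|---|---|
| −2 | −2.80 | 2.68 | 99% |
| −1 | −1.65 | 1.73 | 90% |
| −0.5 | −0.88 | 1.44 | 74% |
| 0 | 0.00 | 1.33 | 50% |
| +0.5 | +0.88 | 1.43 | 26% |
| +1 | +1.65 | 1.73 | 10% |
| +2 | +2.81 | 2.68 | 0.5% |

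The unsigned column is symmetric about zero: shifts of −1 and +1 give 1.73 and 1.73. The last column shows that the share of falls can be almost anything, depending on an input the documents do not supply.

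**5. The same profiles on a signed log-ratio scale**, ln(C_t/C_0):
- 100 to 40: ln 0.40 = −0.916.
- 100 to 160: ln 1.60 = +0.470.
- No change: ln 1 = 0, which is defined.

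The two profiles separate, and the zero shift is no longer a problem.

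**The case against.** The strongest reply is that direction is analysed a few lines away. For each biomarker, SAP 11.4.2.6 compares change from baseline between pooled FDY-5301 and placebo at each timepoint by t-test or Mann-Whitney, and then by dose with ANOVA and Dunnett. SAP 11.1.1 makes that change signed, so a treatment-related fall would show there. That stands, and it limits the point to one supplementary parameter. It does not repair that parameter's own test.

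A second reply is that if nearly all patients' markers rise after the infarction, unsigned and signed values coincide and the comparison is interpretable. That also stands, marker by marker. The documents name no markers, so it cannot be relied on in general.

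Two stronger readings are tempting and should not be made:
- A reader might infer that patients whose marker falls will drop out of the analysis. That follows only from the less natural signed reading. The statement "Missing values will not be imputed" concerns missing data and is not a rule for undefined logs.
- A reader might put a percentage on the patients affected, for instance from the share whose marker peaked before dosing. The documents give no such share, and the condition is the wrong one: a profile of 100, 110, 40 peaks after dosing, yet its largest shift is a fall of 60.

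The SAP Introduction also refers to a separate table-shell document, not available here, which may say more about the derivation.

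**Conclusion.** The point holds, and it is minor. As written, the maximum-deviation comparison is blind to direction on the natural reading and has no rule for zero. On the alternative reading it has no rule for any negative value. Choosing between the readings would be left to programming.

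The reach is narrow. It is one derived parameter of an outcome that Protocol 14.1.6 treats as exploratory secondary, although its tests recur in the ITT and PP populations and by TIMI flow and infarct type. Cmax, AUC0-48, the by-timepoint tests, the primary arrhythmia outcome, CMR and troponin are untouched, and the sample size does not rest on it.

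The conclusion that direction is lost rests only on the definition and the log. Its practical size is undetermined: negligible for a marker that rises in nearly everyone, material for one that often falls from its predose value.

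**What to change.** Amend SAP 11.4.2.6 before database lock:

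- Define maximum deviation as the signed log ratio ln(C_t/C_0) at the post-dose time where |ln(C_t/C_0)| is largest. List the eligible times and say whether the 3-month sample counts.
- Analyse it without a further log transform and back-transform to fold change from baseline.
- If it is not normal, use a rank test, as the section already does for the by-timepoint comparisons. That alternative covers only pooled drug against placebo, so name one for the dose comparisons too (Steel's test is the rank counterpart of Dunnett).
- State a rule for zero and below-quantification values. The rules in SAP 11.6.2 are for PK data and set most such values to zero, which would leave the log ratio undefined.
- In the same edit, remove the geometric mean and geometric CV% planned for changes from baseline, which fail for the same reason.

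The maximum log ratio alone would not do. If Cmax is the post-dose maximum, it equals ln Cmax − ln C_0, largely a repeat of Cmax. For 100, 110, 40 it gives ln 1.10 = 0.095 and misses the fall, whereas the definition above gives −0.916.

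The cost is a few sentences of SAP text and reprogramming one variable, with no new data. There are two downsides. For a marker that rises in some patients and falls in others the measure may be bimodal, so the rank test may be needed. Ratios also weigh falls more heavily than differences do: for 100, 170, 50 the raw scale picks the rise of 70, while the log scale picks the halving (ln 0.5 = −0.693 against ln 1.7 = 0.531).

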11.4.2.5 Serum Levels of Troponin

The troponin AUC₀₋₄₈ will be derived from the serum levels of troponin collected at the following timepoints: Predose, 4, 12, 24 and 48 hours post-study drug. AUC₀₋₄₈ will be calculated using the linear trapezoidal method. Where possible, the derivation will be carried out using actual post-dose times recorded. If actual times are missing, nominal times may be used with sponsor approval.

Summary statistics (also including geometric means and geometric coefficient of variation [CV] %) for the serum levels will be produced by each treatment group and the combined FDY-5301 group for the derived AUC₀₋₄₈. The summary statistics for troponin AUC₀₋₄₈ will be presented in a similar way.

The derived AUC₀₋₄₈ will be logarithmically transformed, and an unpaired Student's T-test will be used analyze its differences between all three FDY-5301 groups (overall) and placebo.

The logarithmically transformed AUC₀₋₄₈ from each group will then be tested using a one-way ANOVA to obtain a common variance followed by a Dunnett's post-test to separately compare each FDY-5301 dose group to placebo.

The arithmetic least squares means of the treatment differences will be back-transformed to provide the geometric means and its 95% confidence interval.

The same summarization and statistical analyses will be repeated by baseline TIMI flow (grade 1 and lower, or, grade 2 and 3) and infarct type (anterior or other).

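### By-timepoint biomarker tests use unadjusted change from predose, and the geometric statistics requested for those changes are undefined once any change is zero or negative

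*SAP*

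**What the plan says.** SAP 11.4.2.6 sets out three separate things for the biomarkers.

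- **Test by timepoint.** For each concentration, "a single pairwise comparison will be performed by timepoint to analyze change from baseline value between all three FDY-5301 groups (overall) and placebo". The method is chosen by a Shapiro-Wilk test: "An unpaired Student's T-test will be used for the pairwise comparison if the data are normally distributed and a Mann-Whitney rank test" otherwise. A one-way ANOVA with Dunnett comparisons of each dose with placebo follows. No covariate and no log transform are stated.
- **Descriptive table.** "Summary statistics (also including geometric means and geometric CV%) for each plasma biomarker concentration will be produced" by treatment group and overall, "for the values and its changes from baseline".
- **Derived parameters.** Cmax, AUC0-48 and maximum deviation are log-transformed, tested by ANOVA with Dunnett, and back-transformed with 95% confidence intervals. No predose covariate is used.

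The baseline is a true pre-treatment value: "The baseline is defined as the last actual value obtained prior to study drug infusion". Protocol 12.2.5 schedules a predose sample, then samples at "1,4,12, 24 and 48 hours post-study drug", and one at 3 months.

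SAP 11.4.2.5 log-transforms troponin AUC0-48 and says a t-test "will be used analyze its differences between all three FDY-5301 groups (overall) and placebo", again without the predose value as a covariate.

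Protocol 14.1.6 calls these analyses exploratory secondary efficacy outcomes. It does not say that biomarkers are to be compared on change from baseline, and SAP section 13 does not list this as a change from the protocol.

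**The concern.** There are two faults, and curing one does not cure the other.

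**Efficiency.** A change score subtracts the whole predose value. If that value predicts the later one poorly, subtraction adds noise; if it predicts strongly with a slope other than 1, subtraction removes the wrong amount. ANCOVA estimates the slope from the data. The analysis set assumed for sample size is 20 placebo patients against 60 on active drug, so precision matters, and the covariate is already being collected.

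**A statistic that may not exist.** A geometric mean is the exponential of a mean of logs, so it needs every observation to be above zero. A change from baseline can be zero or negative, and the SAP has no rule for that. The same difficulty touches the log of maximum deviation. Its definition mentions both a largest-magnitude shift and an absolute change, so its sign is unclear. If signed, falls cannot be logged; if absolute, rises and falls count alike and a zero still fails.

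The by-timepoint tests also give no ratio estimate to carry into a later trial. When Shapiro-Wilk sends the pooled test to Mann-Whitney, the dose comparisons still run on the raw-scale ANOVA.

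**Working it through.** **The plan's own figure.** No power is stated for biomarkers. The nearest laboratory outcome is troponin AUC (SAP section 9: 39% reduction, SD 60%, 20 against 60, 80% power). Standardised effect 39/60 = 0.65; 0.65 × √(20 × 60/80) = 2.517. Power is Φ(2.517 − 1.645) = 80.9% at one-sided 5% and Φ(2.517 − 1.960) = 71.1% at two-sided 5%. The stated 80% is therefore reproduced only one-sided; the documents give neither alpha nor sidedness. This fixes the design (20 against 60) but says nothing about r or k.

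**Variance ratio on one scale.** Set the later SD to 1 and the predose SD to k.

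- Change score variance: 1 + k² − 2rk
- ANCOVA variance: 1 − r²
- First minus second: (r − k)², which is never negative. So ANCOVA is never worse in large samples (apart from 1 degree of freedom), and the two are equal when r = k.

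Reduction in variance, 1 − (1 − r²)/(1 + k² − 2rk), for assumed r and k:

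| k | r = 0.2 | r = 0.5 | r = 0.8 |
|---|---|---|---|
| 1 | 40% | 25% | 10% |
| 0.5 | 8.6% | 0% | 20% |
| 0.25 | 0.3% | 7.7% | 46% |

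Example, k = 0.25 and r = 0.2: 0.96/0.9625 = 0.997.

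**Power, k = 1.** If the change score had 80% power (two-sided 5%, 20 against 60), ANCOVA would have 93.5%, 89.9% and 86.0% at r = 0.3, 0.5 and 0.7.

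**The SAP rule itself.** The table compares methods on one scale, whereas the proposal also moves from raw to log. So lognormal data were simulated (20 against 60, two-sided 5%, 1,500 runs per scenario), comparing the Shapiro-Wilk rule on raw change with ANCOVA on logs. With assumed CV 60%, a 30% reduction and r = 0.5:

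| Rise over predose | SAP rule | Log ANCOVA |
|---|---|---|
| none | 55% | 80% |
| 2-fold | 76% | 80% |
| 5-fold | 78% | 82% |

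Over 18 scenarios (CV 60% with a 30% reduction, CV 100% with a 39% reduction; r = 0.2, 0.5, 0.8; no, 2-fold and 5-fold rise), ANCOVA led by about 2 to 32 points. Type I error was about 5% for both. Much of the largest gain is not due to the covariate. At CV 100%, r = 0.2 and no rise, the SAP rule had 31.9%, the log value with no covariate 63.1%, and log ANCOVA 63.5%.

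**Already-logged parameters.** For Cmax, AUC0-48 and troponin AUC0-48 the comparator is unadjusted, so the reduction is r²: 4%, 25% and 64% at r = 0.2, 0.5 and 0.8.

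**Undefined geometric statistics.** If a share q of patients shows no rise, P(at least one non-positive change among 20) = 1 − (1 − q)²⁰. This is 64% at q = 0.05 and 88% at q = 0.10 (q assumed). In the simulation, at least one of 80 patients had a non-positive change in essentially every run with no rise or a 2-fold rise, and in 1% to 100% of runs with a 5-fold rise.

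**The case against.** The strongest reply is that the planned test is valid: its type I error is about 5%, biomarkers carry no stated power, and no decision rule rests on them. That stands, and it limits this to an efficiency and reporting point.

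Three stronger readings are tempting, and the documents do not support them.

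- A reader might infer that testing change makes the planned geometric means undefined. It does not. The request sits in a separate descriptive sentence and fails only for changes. Geometric means of positive observed values, Cmax and AUC0-48 are well defined.
- A reader might infer that biomarker results cannot be carried forward as ratios. Cmax and AUC0-48 are already analysed on the log scale and back-transformed, as is troponin AUC0-48. Only the by-timepoint tests lack a ratio.
- A reader might take 40%, 25% and 10% as the size of the loss. Those figures need equal predose and later SDs on one scale, and do not apply when Mann-Whitney is used. If concentrations rise sharply after predose, k well below 1 is plausible on the raw scale, and the gain could be almost nothing or larger than those figures.

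It is also fair to say that if predose values correlate weakly with later ones, adjusting the AUC and Cmax models gains little: 4% at r = 0.2. Nor is the change wholly without cost. Logs need a rule for values below quantification, and the SAP's only such rules are for pharmacokinetics, where most such values become zero.

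**Conclusion.** The point holds in two limited parts.

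1. The by-timepoint comparison leaves a scheduled pre-treatment covariate unused. ANCOVA cannot be less efficient in large samples, apart from 1 degree of freedom. The size of the gain cannot be fixed from the documents, because r, k, the biomarker CVs and the effects are all assumed here. It runs from near nil, when r is close to k, to 40% of the variance at k = 1 and r = 0.2, and 46% at k = 0.25 and r = 0.8.
2. The geometric mean and geometric CV% of raw changes are wrong as specified. This needs no assumption about effect size: one zero or negative change is enough. Only how often it would happen is assumed.

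The planned test is not invalid, and the other geometric summaries are sound. As biomarkers are exploratory and unpowered, this is a modest improvement that should be made while the SAP can still be edited.

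**What to change.** In SAP 11.4.2.6 and 11.4.2.5:

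1. For each biomarker and timepoint, fit an ANCOVA of log(value) on treatment (four levels) plus log(predose value). Take both the overall FDY-5301 contrast with placebo and the Dunnett comparisons from it, as geometric mean ratios with 95% confidence intervals.
2. Add the log predose covariate to the existing models for log Cmax, log AUC0-48 and log troponin AUC0-48.
3. Replace the geometric mean and geometric CV% of the raw change by the geometric mean ratio to predose.
4. Define maximum deviation so that it can be logged, for example as a log ratio to predose, or do not log it.
5. State a rule for biomarker values below quantification, for example a fixed fraction of the lower limit.

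Missing predose values should not be filled in: Protocol 14.1.1 and SAP 11.1 rule out imputation. The timepoint tests lose no one by this, because a change score already needs the predose value. A patient without one would drop out of the adjusted Cmax model, so the number excluded should be reported.

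The cost is SAP wording and programming, 1 degree of freedom per model, and an estimate that is a ratio rather than a difference. No new samples are needed. SAP section 13 should record the choice.
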